### 2.8.1.1 Adverse events of special interest / grouping of AEs

Specific groupings of AESI will be considered and the number of patients with at least one event in each grouping will be reported. Such groups consist of AEs for which there is a specific clinical interest in connection with deferasirox treatment or AEs which are similar in nature (although not identical). Note that certain AEs may be reported within multiple groupings.

All AESI groupings are defined through the use of Preferred Terms (PT), High Level Terms (HLT), System Organ Classes (SOC), Standardized MedDRA Queries (SMQ), Novartis MedDRA Queries (NMQ), or through a combination of these components.

The AESI search table will be used to map reported AEs to the notable AE groupings. The list of AESIs may be updated during the course of the study based on accumulating safety data. Therefore, the clinical study report will list the AE groupings used and provide a listing of the corresponding AESI search table.

Note that certain AEs may be reported within multiple groupings.

For AESIs, time-to-event analysis will be performed as appropriate. Results will be tabulated and the Kaplan-Meier estimates for the cumulative rate will be plotted.

## 2.8.2 Deaths

Separate summaries and listings will be provided for deaths for each treatment period (core and extension).

## 2.8.3 Laboratory data

The summary of laboratory evaluations will be presented for different groups of laboratory tests (hematology, serum chemistry, serum ferritin, serum creatinine, and urinalysis) for different treatment periods (core and extension). Descriptive summary statistics for the change from baseline to each study visit will be presented. These descriptive summaries will be presented by test group, laboratory test and treatment group. Change from baseline will be summarized only for the patients who have both baseline and post-baseline assessment. For each parameter, maximum change from baseline within each study period will be evaluated analogously.

In addition, shift tables will be provided for all parameters to compare a patient's baseline laboratory evaluation relative to the visit's observed value. For the shift tables, the normal laboratory ranges will be used to evaluate whether a particular laboratory test value was normal, low, or high for each visit value relative to whether or not the baseline value was normal, low, or high. These summaries will be presented by laboratory test and treatment group. Shifts will be presented by visit as well as for most extreme values post-baseline.

Grading of laboratory values will be assigned programmatically as per NCI Common Terminology Criteria for Adverse Events (CTCAE). The calculation of CTCAE grades will be based on the observed laboratory values only, clinical assessments will not be taken into account.

CTCAE Grade 0 will be assigned for all non-missing values not graded as 1 or higher. Grade 5 will not be used.

For laboratory tests where grades are not defined by CTCAE, results will be categorized as low/normal/high based on laboratory normal ranges.

The following summaries will be generated separately for hematology and biochemistry tests:

- Reporting of all laboratory data with values flagged to show the corresponding CTCAE grades if applicable and the classifications relative to the laboratory normal ranges ([Table 5.3.1](#))

For laboratory tests where grades are defined by CTCAE

- Worst post-baseline CTCAE grade (regardless of the baseline status). Each patient will be counted only once for the worst grade observed post-baseline.
- Shift tables using CTCAE v4.3 grades to compare baseline to the worst on-treatment value

For laboratory tests where grades are not defined by CTCAE

- Shift tables using the low/normal/high/ (low and high)
- Classification to compare baseline to the worst on-treatment value. Apart from the above laboratories summaries, summaries of Hepatitis Viral tests will also be performed.

In addition, a summary of serum ferritin will be presented by TDT and NTDT patients, by age group, and ICT-naive vs. ICT patients by visit.

For all lab assessments, the baseline of each period will be considered based on the actual baseline or start of that particular period, as applicable. Also the baseline data for FCT phase will be provided for only the number of patients available in the analysis set at the start of the period.

## **2.8.4 Other safety data**

### **2.8.4.1 ECG and cardiac imaging data**

Abnormalities of ECG parameters will be summarized together with an overall interpretation of the findings at screening and end of core phase, i.e. at Week 48. The following quantitative variables will be summarized: QTcB interval, QTcF interval, heart rate, PR interval, QT interval, QRS duration.

Number and percentage will be provided for the patients who have clinically significant abnormalities present.

Summary statistics will be presented for ECG variables at baseline and at end of core phase i.e. at Week 48. In addition, shift tables comparing baseline ECG interpretation (normal, abnormal, not available, total) with the Week 48 interpretation (normal, abnormal, not available, total) will be provided. A listing of all newly occurring or worsening abnormalities will be provided, as well as a by subject listing of all quantitative ECG parameters.

### **2.8.4.2 Vital signs**

Measurements of vital signs and body weight done more than 30 days after discontinuation of study medication, will be excluded from the analysis but will be listed.

The change from baseline in diastolic blood pressure, systolic blood pressure, pulse rate, and weight will be summarized by scheduled visit with n, mean, SD, minimum, median, and maximum values.

A listing will be provided for all vital signs and weight. Notable vital signs and weight values are flagged.

### **2.8.4.3 Auditory, ocular, and chest X-ray interpretation**

Auditory, ocular, and chest X-ray overall interpretation will be summarized by normal, clinically insignificant abnormality, and clinically significant abnormality, with number and percentages.

## **2.9 Pharmacokinetic endpoints**

Not applicable.

## **2.10 PD and PK/PD analyses**

Not applicable.

## **2.11 Patient-reported outcomes**

The following PROs will be summarized using FAS.

### **Preference questionnaire**

The preference questionnaire is a three item questionnaire. There are three separate versions depending on the week(s) that the questionnaire is administered. Week 4 and 24 contains preference questions on DT and iron chelators, Week 28 contain questions on all three medications and Week 48 on DT and FCT only.

Summaries of the preference questionnaires will be performed at Visits 4, 24, 28 and 48, if data is available, in Core phase of the study and additionally from the data collected at the time of immediate next visit based on patients who had treatment switching. No total score is calculated on the preference questionnaire. Each item will be scored as the proportion of patients who select each response option.

The analysis of preference data has been explained in [Section 2.5](#) and [Section 2.7](#).

### **Palatability using PRO/ ObsRO questionnaire**

The palatability questionnaire consists of 4 items. Two items measure the taste and aftertaste of the medication and are scored on a 5 point response scale. The remaining palatability items refer to whether the medication was taken (i.e. swallowed or vomited) and how the patient perceived the amount of medication to be taken.

For the palatability questionnaire the overall score will be constructed using a scoring matrix from the score of items. Standard descriptive analyses including absolute and relative changes will be performed for both formulations (DT/FCT) for the overall score at Week 4, Week 24, Week 28 and Week 48 and overall score at Screening for iron chelators. The baseline data for treatment period 1 and 2 will be Week 4 and Week 24 data respectively, only one assessment is observed at Screening period. The summary will be provided separately for PRO and ObsRO patient groups.

The standard descriptive analyses include: n, mean, standard deviation, minimum, median and maximum. The 95% CI for the absolute and relative (or difference) change from baseline of the overall score will also be presented for the treatments.

### **mSICT using PRO / ObsRO questionnaire**

The Modified SICT (mSICT) questionnaire consists of 15 items for the PRO version and 22 items for the ObsRO version that represent 3 domains; Adherence, Preference and Concerns.

For the mSICT questionnaire, the score for each domain based on the 15 questions common to both the PRO and ObsRO versions, will be the mean of the score of items included in the corresponding domain. The additional 7 questions that are included in the ObsRO version will be scored as standalone items. Standard descriptive analyses will be performed for both formulations (DT/FCT) for each domain score at Week 4, Week 24, Week 28 and Week 48, and at Screening for iron chelators. The baseline data for treatment period 1 and 2 will be Week 4 and Week 24 data respectively, only one assessment is observed at Screening period. The summary will be provided separately for PRO and ObsRO patient groups.

Weighted mean of both groups will also be reported to highlight the combined result. Separately weighted mean of both the groups for 15 common questions will also be reported. Pooled SD will be provided only if the data from both the groups follow the same distribution.

The standard descriptive analyses include: n, mean, SD, minimum, median and maximum. The 95% CI for the absolute and relative (or difference) changes from baseline in all domains will be presented for the treatments.

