7.3.1 Preference Questionnaire

The preference questionnaire is a four item questionnaire. There are four separate versions depending on the week(s) that the questionnaire is administered.

For week 48 (primary endpoint) the first item asks the patients (or parents of young patients from 2 to 9 years old) which medicine they are currently taking with the response options: "Tablet to dissolve in liquid", "Film coated tablet ", "Sprinkle powder on food" and "I don't know". The second item asks which of the medicines did the patient "Like best" with the same response options as that of the first item. Finally, the third item asks the patient why he/she preferred the medicine they chose.

For week 28 the first item asks patients to choose from the following medicines: “Tablet to dissolve in liquid”, “Film coated tablet (taken once a day)”, “Tablet (taken 3 times a day)”, “Sprinkle powder on food”, “Injection” and “I don’t know”. The second items remain the same asking which medicine the patients like the best (out of the above response options). Similarly the third item remains the same.

For weeks 4 and 24 the first item asks patients to choose from the following medicines: “Tablet to dissolve in liquid”, “Tablet (taken 3 times a day)”, “Injection” and “I don’t know”. The second items remain the same asking which medicine the patients like the best (out of the above response options). Similarly the third item remains the same.

The following preference attributes are provided:

- Taste
- Aftertaste (taste left in your mouth after you swallow)
- Convenience (it’s not a problem to take your medicine - administration)
- Number of pills
- No/Less side effects
- Can correctly prepare the medicine
- Easier to remember to take the medicine
- Number of times you have to take the medicine
- No/Less pain on the injection site
- Gain my personal time with family and friends
- Other _____

The questionnaire is administered at week 4, week 24, week 28 and week 48. No total score is calculated on the preference questionnaire. Each item will be scored as the proportion of patients who select each response option.

7.3.2 mSICT – patients greater or equal to 10 years old

The Modified SICT (mSICT) questionnaire consists of 15 items that represent 3 domains; Adherence, Preference and Concerns.

The adherence domain consists of 7 items, 6 of which are measured using a 5 point response scale.

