Items 4, 5 and 6 use the response format 1 “Never”, 2 “Rarely”, 3 “Sometimes”, 4 “Most of the time”, 5 “Always”; Item 7 uses the response format 1 “Very easy”, 2 “Easy”, 3 “Neither easy nor hard”, 4 “Hard” and 5 “Very hard”; Items 8 and 9 use the response format 1 “Very bothered”, 2 “Quite bothered”, 3 “Moderately bothered”, 4 “A little bothered” and 5 “Not bothered at all”. An Adherence domain score will be calculated by summing these 6 items and as a result a higher score will indicate worse adherence.

Item 10 captures the reasons that the patient did not always take their medication as instructed and is only asked for patients who, at Item 6, indicated that they did not “Always” take their medication as instructed. These patients are instructed to choose all reasons that apply. Each response category will be coded as a binary item, for example taste will be an item with the

response format 0 “Not endorsed”, 1 “Endorsed”. For the “other” option, if there is a common response (>10%) it will be included as an additional binary response category in the analysis, otherwise other will be treated as Other 0 “Not endorsed”, 1 “Endorsed”. This item will be used as a standalone item to better understand the overall Adherence domain.

Satisfaction/preference domain consists of 3 items, 2 assess the patients’ satisfaction with the medication and are measured using a 5 point response scale with the response format: 1 “Very satisfied”, 2 “Satisfied”, 3 “Neither satisfied nor dissatisfied”, 4 “Dissatisfied”, 5 “Very dissatisfied”. A Satisfaction domain score will be calculated by summing these two items. Higher scores will indicate worse satisfaction.

The third item asks the patients to assess which medication for iron overload they prefer; this item will be used as a standalone item in the clinical trial.

Concerns domain consists of 3 items to address any concerns and worries the patient has with their medication. All 3 items are measured on a 5 point response scale with the response format 1 “Always”, 2 “Most of the time”, 3 “Sometimes”, 4 “Rarely” and 5 “Never”. A Concerns domain score will be calculated by summing these 3 items. Higher scores will indicate fewer concerns.

Two additional items (items 14 and 15) will also be scored as standalone items. Item 14 asks patients to choose attributes pertaining to why they chose to prefer a certain medication. Item 15 asks patients to “rank order” the medicines they have taken.

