7.3.3 Observer Reported mSICT – patients less than 10 years old

Similar to the mSICT for patients greater than 10 years old, an observer reported mSICT will be administered to those patients who are 2-9 years old. Parents or caregivers of these patients will complete the mSICT for behaviors that are observed. The items are similar to the original mSICT however item 15 (the ranking exercise) is not included. In addition, there are 7 items asking the parent to respond from their perspective regarding:

- Feeling worried
- How often medication was given for iron over load
- Thinking to stop giving medication for iron overload
- Following the doctor’s instructions
- Reasons why not always giving medication
- Ease of administrating medication
- Bothered by time it took to administer medication

Adherence, satisfaction/preference and concerns domain scores (which are the same as above) and items will be summarized using standard descriptive statistics (Screening, week 4, week 24, week 28 and week 48).

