For the palatability questionnaire the overall score will be constructed using a scoring matrix from the score of items. Standard descriptive analyses including absolute and relative changes will be performed for both formulations (DT/FCT) for the overall score at Week 4, Week 24, Week 28 and Week 48 and overall score at Screening for iron chelators. The baseline data for treatment period 1 and 2 will be Week 4 and Week 24 data respectively, only one assessment is observed at Screening period.

The standard descriptive analyses include: n, mean, standard deviation, minimum, median and maximum. The 95% confidence interval for the absolute and relative (or difference) change from baseline of the overall score will also be presented for the treatments. In addition to that, summaries will also be performed from the data collected at the time of immediate next visit based on patients who had treatment switching.

Details about scoring and further analyses will be included in the SAP.

mSICT

The Modified SICT (mSICT) questionnaire consists of 15 items that represent 3 domains; Adherence, Preference and Concerns.

For the SICT questionnaire, the score for each domain will be the mean of the score of items included in the corresponding domain. Standard descriptive analyses will be performed for both formulations (DT/FCT) for each domain score at Week 4, Week 24, Week 28 and Week 48 and at Screening for iron chelators. The baseline data for treatment period 1 and 2 will be Week 4 and Week 24 data respectively, only one assessment is observed at Screening period.

The standard descriptive analyses include: n, mean, standard deviation, minimum, median and maximum. The 95% confidence intervals for the absolute and relative (or difference) changes from baseline in all domains will be presented for the treatments. In addition to that, summaries will also be performed from the data collected at the time of immediate next visit based on patients who had treatment switching. .

Details about scoring and further analyses will be included in the SAP.

GI symptoms

The GI symptom consists of 6 items, 5 of which are scored using a 0 – 10 rating scale with item appropriate end anchors to rate the symptom, The sixth item assesses bowel movement frequency during the past 24 hours, using 7 response options.

The GI symptoms will be summarized as analogous to the above questionnaires. Details about scoring and further analyses will be included in the SAP.

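### The mSICT domain scores are sums in Protocol 7.3.2 but means in Protocol 10.5.6 and SAP 2.11, the items to be scored are not listed, and the SAP's item counts conflict with Protocol 7.3.3

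*SAP*

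**What the plan says.** Protocol 7.3.2 introduces the instrument: "The Modified SICT (mSICT) questionnaire consists of 15 items that represent 3 domains; Adherence, Preference and Concerns". For adherence, "The adherence domain consists of 7 items, 6 of which are measured using a 5 point response scale"; those six (items 4 to 9) are summed. Item 10, the reasons for not taking the medicine as instructed, is standalone. The satisfaction/preference domain has three items: "A Satisfaction domain score will be calculated by summing these two items", while the third asks which medicine is preferred and "this item will be used as a standalone item in the clinical trial". Concerns is the sum of three items. Items 14 and 15 are also standalone.

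Protocol 7.3.3 describes the observer form for ages 2 to 9. It says the domain scores are the same and the items similar, "however item 15 (the ranking exercise) is not included", and it adds 7 items answered from the parent's perspective.

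Protocol 10.5.6 says "the score for each domain will be the mean of the score of items included in the corresponding domain" and leaves scoring details to the SAP. SAP 2.11 repeats the mean rule ("will be the mean of the score of items included in the corresponding domain"), bases it on 15 questions said to be common to both versions, and gives "15 items for the PRO version and 22 items for the ObsRO version". It makes only the 7 extra observer items standalone. It plans a weighted mean of the patient and observer groups, and a separate one over the 15 common questions. Neither section lists the items in each domain. SAP section 4 records no change from the protocol's analyses.

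**The concern.** The satisfaction endpoint is the absolute and relative change in SICT domain scores between the FCT, DT and prior-chelation periods (Protocol Table 3-1, SAP Table 1.2.1). A sum and a mean put absolute change on different scales, and the documents prescribe both.

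Item membership is also left open. Protocol 7.3.2 gives the domains 7, 3 and 3 items but scores only 6, 2 and 3 of them. A rule that averages the items in a domain, without repeating the exclusions, can be taken to include the other two. One is a choice of medicine, which has no numeric order. The other is a tick-all list asked only of patients who did not answer *Always* at item 6. If the medicine code entered the satisfaction score, the score could move when the preferred formulation changed and satisfaction did not.

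Finally, a weighted mean over 15 common questions cannot be produced in full if one of the 15 is absent from the observer form.

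**Working it through.** **1. Item counts.** Inputs: domain sizes 7, 3 and 3 plus items 14 and 15 (Protocol 7.3.2); item 15 omitted and 7 items added for observers (Protocol 7.3.3).

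- Patient version: 7 + 3 + 3 + 2 = 15. This reproduces the figure in both documents.
- Common items: 15 − 1 = 14. The SAP says 15.
- Observer version: 14 + 7 = 21. The SAP says 22, which is reached only as 15 + 7, that is, with item 15 kept.
- Scored items under 7.3.2: 6 + 2 + 3 = 11. Item 15 is not among them.

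**2. Sum against mean, same items, complete data.** For k items, sum = k × mean.

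| Domain | k | Range of sum | Range of mean | Ratio of absolute changes |
|---|---|---|---|---|
| Adherence | 6 | 6 to 30 | 1 to 5 | 6 |
| Satisfaction | 2 | 2 to 10 | 1 to 5 | 2 |
| Concerns | 3 | 3 to 15 | 1 to 5 | 3 |

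Confidence limits for absolute change scale by the same k. Relative change is unaffected, because k cancels. If both satisfaction items go from 4 to 2, the sum goes from 8 to 4 and the mean from 4.0 to 2.0; both are −50%.

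**3. Missing items.** Take a patient who answers 3 throughout adherence. With all six items the sum is 18 and the mean 3.0. With one item missing and the rest scored, the sum is 15 and the mean is still 3.0. The documents say missing data are not imputed, but give no rule on whether an incomplete mSICT domain is scored.

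**4. Literal three-item satisfaction mean.** The documents give no numeric code for the preferred medicine, so the codes here are assumptions. Both satisfaction items go from 4 to 2, so the two-item change is −50%. Codes of 1, 3 and 6 were tried before and after; the extremes were:

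- code 6 then 1: (8 + 6)/3 = 4.67 to (4 + 1)/3 = 1.67, a change of −64%;
- code 1 then 6: (8 + 1)/3 = 3.00 to (4 + 6)/3 = 3.33, a change of +11%.

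With both satisfaction items fixed at 2, a code moving from 1 to 2 takes the mean from 5/3 = 1.67 to 6/3 = 2.00, or +20%. Reversing the codes gives 2.00 to 1.67, or −17%. Size and sign come from the coding alone.

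**5. Direction within adherence.** Under 7.3.2, *Always* = 5 at item 6 (taking the medicine as instructed) is good adherence; *Very hard* = 5 at item 7 is unfavourable; *Not bothered at all* = 5 at items 8 and 9 is favourable. The section nevertheless says that a higher total is worse and gives no reverse coding. The wording of items 4 and 5 is not in the documents, so their direction cannot be judged.

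**The case against.** The strongest reply is that item membership is already settled. Neither mean rule refers to all items in the domain. SAP section 1 follows the protocol's algorithms and conventions unless otherwise specified, and 7.3.2 plainly makes item 10 and the preference item standalone. A careful programmer would exclude them, and item 10 has no single score to average in any case. This largely stands. A reader might infer that the plan puts the preference item into the satisfaction score; the documents support only that it could be read that way. Deferring to the protocol does not settle sum against mean, because the SAP does specify a mean and the protocol contradicts itself.

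Second, with complete data the choice of sum or mean is a change of units. That stands for relative change. It does not help absolute change and its confidence interval, which are also to be reported, or incomplete questionnaires.

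Third, a reader might infer that the wrong count spoils the pooled domain scores. It does not: item 15 belongs to no domain score, and on the protocol's account the 11 scored items are shared. The SAP also reports the two groups separately. Only the weighted mean over 15 common questions is affected.

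Fourth, a reader might infer that 14 and 21 are the true counts. The form is not in the documents, and the SAP amendments of 2020 and 2021 are later than the 2019 protocol amendment. The texts show a conflict, not which count matches the form in use.

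**Conclusion.** The contradiction is real and should be removed. Protocol 7.3.2 prescribes sums of named items; Protocol 10.5.6 and SAP 2.11 prescribe means without naming the items. Absolute changes differ by factors of 6, 2 and 3, and the two rules part further when items are missing. The SAP's 15 and 22 do not fit Protocol 7.3.3. The adherence score in 7.3.2 also mixes item directions.

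The consequence is limited. SAP 2.7.2 plans no formal testing of secondary endpoints and the mSICT analysis is descriptive; the primary test and the sample size are untouched. No single percentage for distortion by the preference item, such as the 20% above, can be taken as an estimate, since it rests on assumed codes and on a reading that the documents allow but do not require.

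**What to change.** In SAP 2.11 and Protocol 10.5.6:

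- State one scoring rule, for example the mean of the 6, 2 and 3 items named in Protocol 7.3.2, and bring 7.3.2 into line with it.
- List the scored items by number for the patient and observer versions.
- State that item 10, the preference item and items 14 and 15 are standalone.
- Give the reverse coding needed for all adherence items to run the same way, after checking items 4 and 5 on the form.
- Add a rule for domains with missing items.
- Reconcile the 15 and 22 against the actual form, and limit the patient/observer weighted mean to the 11 scored items.
- Record the clarification in SAP section 4 with its date, since the current SAP version follows the Week 48 database lock.

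The cost is wording and some reprogramming; no new data are needed.
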